1. STUDY DESIGN

Study design

This is a multicenter single-arm intervention study with a pre- and post-training test, supplemented with enriched nutrient intake. The study will be executed in accordance with the declaration of Helsinki and is registered in ISRCTN registry under reference number 10008907. Written informed consent (IC) will be obtained from all participants.

Participants

Patients >18 years with an indication for AAA-repair will be included in the Treant Hospital (Emmen, Hoogeveen, and Stadskanaal) and in the Wilhelmina Hospital in Assen. This study was designed in close cooperation with the University Medical Center Groningen (UMCG). Patients with an elective indication for operation will be included in this study. Patients will be excluded with an indication for operative intervention within three weeks (semi-elective), patients with connective tissue disorders (e.g., Marfan), patients evaluated unfit for training, and patients unable to understand the meanings of this research.

Recruitment

Consecutive patients with an indication for an aneurysm repair will be asked to participate by their treating physician. The investigator or one of the members of the research team will collect the IC. They will complete a questionnaire with the help of a research nurse and will be assessed for initial eligibility by means of a cardiopulmonary exercise test at the sports medicine office, under the responsibility of the principal investigator (Figure 1). Patients unable to train as indicated by the specialist in sports medicine and/or the cardiologist, will receive necessary medication, and will be excluded. After this judgement, subjects evaluated fit for training, receive the home monitor (pulse oximeter and sphygmomanometer (SMM)) and an explanation how to use the home monitoring app Luscii and FortiFit. The explanation concerning the use of the monitors and FortiFit will be given to the accompanying spouse and/or caregivers, as well. Subjects evaluated unfit for training will receive additional information and follow up by the cardiologist. If, during this follow up, patients medical condition improves, training will be promptly started.

Following the explanation, patients have their intake with a physical therapist. The patients able to perform training, will be prescribed a personalized exercise program and will be followed by a local physical therapist. This includes a training scheme for exercises at home (Appendix 2). They will be asked to train at home and once a week at the physical therapist, check their vital sings with the pulse oximeter and de SMM, and communicate these vital

Version number: 4

signs with the Luscii app to a call center Altide. In case of previously set limitations, this call center will contact the hospital (Appendix 3).

Home-monitored training

All eligible patients will participate in a three-to-nine-week (average of six weeks), partly supervised, home-monitored training program prior to elective AAA-repair. The second CPET measurement is planned after the training program. Training frequency during the prehabilitation will be five sessions per week including a weekly evaluation by the physical therapist. Training sessions at home are prepared and should be able to be performed without extra adjuncts (see below). Before and after home-monitored training sessions without a physical therapist, subjects communicate oxygen saturation, heartrate, blood pressure, number of steps (nS), and number of smoked cigarettes through the Luscii app. According to these measurements, automatic advises will be given through the app (Appendix 3).

To evaluate a difference after the average of six weeks, subjects visit the specialist in sports medicine a second time to perform a CPET. Depending on the performance of patients in relation to the improvement in this second CPET, a subdivision of an improved and a stable (not improved) group will be made. It is expected that improved patients will show an increase of their VO2 at VAT of 1,5 ml/kg/min or more.

Three months after surgery, monitoring is complete, and preoperative patient characteristics of the groups will be compared.

Home-monitored exercises

Four times a week subjects perform exercises at home, preceded and followed by communication of preset parameters through the Luscii app. These exercises include stair-climbing and sit-to-stand exercises (high-intensity), as well as outdoor cycling, outdoor walking, and outdoor running (moderate intensity). The combination will be assembled in close collaboration between the physical therapist and the specialist in sports medicine, under the responsibility of the principal investigator. Through registration and monitoring activities by the patient, the physical therapist will be able to advise activities performed at home. The physical therapist will discuss these findings with the patient on a weekly base and adjust the scheme in relation to physical improvement.

Once a week subjects perform a steep ramp test performance to estimate aerobic fitness, under the supervision of the physical therapist. This test is used to optimize training intensity of the interval and endurance training sessions, as well as to monitor progression.

Nutritional supplementation

Version number: 4

To support muscle protein synthesis, participants will be provided with protein supplementation immediately following exercise and (approximately 30 minutes) before sleep, providing a standard dosage of 30 g of a high-quality (whey and casein) protein that contains at least 10 g of essential amino acids, of which 2-3 g Leucine. Since vitamin D is associated with muscle mass and muscle strength. It will be supplemented daily according to guidelines of the Health Council of the Netherlands (10 μ g for woman aged 50-69 years, for men <70 years and women <50 years with colored skin and/or little sun exposure, and 20 μ g for women and men aged 70 years or older)(14, 15). To prevent patients from having a deficiency of vitamins and minerals below recommended doses before surgery, all other vitamins and minerals are supplied in a multivitamin/mineral supplement containing 50% of the recommended daily allowance (13).

[figure not shown]

Figure 1: flow chart (https://app.diagrams.net) concerning the references of patients. FT= physical therapy, CPET= cardiopulmonary exercise test, HLOS= hospital length of stay.

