Nature and extent of the burden and risks associated with participation, benefit and group relatedness: Patients will be asked to fill out a questionnaire with a research nurse and visit a cardiologist and a specialist in sports medicine preceding their training. During their three-to-nine weeks preoperative period, patients will be asked to train. This will be tiresome but rewarding; we expect to accomplish an increase in physical fitness. The elderly seem capable of performing home monitoring. The extra energy and proteins necessary for the training will be substituted with extra FortiFit®. These substitutes help patients to get into an anabolic condition, preoperatively. Apart from the extra consultations and the training the patient will not undergo extra laboratory tests other than necessary for regular AAA surgery. The risks are minor, for it has been proven safe to train patients indicated for elective AAA surgery in advance. Still, we wish to monitor at home, and training is prohibited outside office hours. This enables the research team to educate patients in health-related issues (heart rate recovery) and virtual hospital contact, earlier described as a Surgery School. Furthermore, it is expected that patients are encouraged by the virtual feedback. Risk benefit analysis: the risks of causing harm are small, because patients will be physically evaluated before training starts and will be monitored for safety throughout the program. The benefits may be substantial for improving surgical outcome, patients have been taught to train in their living context, and home monitoring improves extramural communication and ease hospital capacity issues.

INTRODUCTION AND RATIONALE

Abdominal aneurysms (AAAs) affect a range of 1.9-18.5% of men and less than a quarter in women (1). In recent years the mortality rate is declining (2-4) and thirty-day mortality rate of an elective repair remains at 2-3% and higher for women (5).

Cardiopulmonary evaluation assesses operative risks in patients undergoing AAA surgery (6, 7). The decrease of operative mortality was mainly due to technical innovations (4), but no attention has been paid to fitness of patients. Preoperative exercise training improves aerobic fitness (e.g., the oxygen uptake (VO₂) at the ventilatory anaerobic threshold (VAT)) (7).

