6.3. Study procedures

Patients with an indication for AAA repair are routinely prepared for this operation with a visit at the anesthesiologist and the cardiologist. After the indication is set, the minimal waiting time for the operation is usually six weeks on average. This gives the

Version number: 4 21 of 41

subject the opportunity to start training. Surgery will not be postponed for this pilot study.

After the indication and informed consent, a questionnaire will be completed with the help of a professional research-nurse, and a cardiologic consultation will be performed. When subjects are fit for training, they will be informed about the use of the home-monitoring device. This will be followed by a visit at physical therapist (Figure 1).

Estimation of costs Aneurysm in motion					
	WZA (40	patients)	Treant (60 p	Totals	
Intake Luscii	€ 32	€ 1.280	€ 32	€ 1.920	€ 3.200
Alert Luscii	€ 14,70	€ 588	€ 14,70	€ 882	€ 1.470
Costs research bureau (30 minutes)	€ 20	€ 800	€ 20	€ 1.200	€ 2.000
	Totaal 1 jaar	€ 2.668		€ 4.002	
Both hospitals					€ 6.670

Table 2: Expected costs in participating hospitals, without insurance costs.

Following these three explanations (home monitoring, questionnaires, and training), the subject will be asked to start their home training during office hours, following a communication with the communication center of the home monitoring (Luscii). After each training and cooling down, parameters should be imported from the homemonitoring device and feedback will be given from the communication center. In case of anomalous measurements, the hospital will be contacted.

	Action	Conditions	Requirement Fit patients	Requirement Unfit patients
Inclusion criteria	Indication AAA repair	Elective repair	Eligible for inclusion	Eligible for inclusion
Inc	Informed consent	Signed	Eligible for inclusion	Eligible for inclusion
	Questionnaire	Various characteristics	One hour	One hour
	Specialist sports medicine	Consultation and CPET	One hour	-
	Cardiologist	Safe to perform training	Questionnaire and CPET	-
		Unsafe	-	Follow up
ıction	Explanation	Home monitoring device	One hour	-
Introduction	First visit physical therapist	At location physical therapist	One hour	-
iks	Daily training at home	Four days a week	Four hours	-
3-9 weeks	Weekly visit physical therapist	Once a week	One hour	-
Postop	Three months after the operation	Outpatient clinic	Ten minutes	Follow up

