11. STRUCTURED RISK ANALYSIS

11.1. Potential issues of concern

a. Level of knowledge about mechanism of action

Previous studies have investigated the risk of training in AAA patients (8, 9, 27, 28) and in patients with a thoracic aorta aneurysm (TAA)(29). These studies do not report mortality due to training or exercise. Thanks to the change in preoperative management, patients are offered home monitoring to intensify daily communication with the hospital, and to enhance safety.

b. Previous exposure of human beings with the test product(s) and/or products with a similar biological mechanism

Human beings with an AAA have been exposed to exercise previously.

c. Can the primary or secondary mechanism be induced in animals and/or in *ex-vivo* human cell material?

Not applicable

d. Selectivity of the mechanism to target tissue in animals and/or human beings

Not applicable

e. Analysis of potential effect

The potential effect of exercise is improvement of condition. A side effect might be elevation of blood pressure, but it is expected to contain the aneurysm, as no side effect have been mentioned previously (see section 10.1a as well).

f. Pharmacokinetic considerations

Not applicable

Version number: 4 31 of 41

g. Study population

Patients with an indication for AAA repair, endovascular or open. Standard care is performed. Subjects are asked to improve their condition with exercise training.

h. Interaction with other products

Not applicable

i. Predictability of effect

Not applicable

j. Can effects be managed?

Due to home monitoring and weekly follow up by the physical therapist, effects of the training are followed closely. In case of deterioration, treating physician will be contacted. Either through the Luscii app, by email or by telephone.

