Appendix 3; Automatized answers Luscii.

Pulsoximeter		
Eerste meting (voor de training)	Zuurstofsaturatie 95 of lager	even rustig zitten, haal een paar keer diep adem en meet je zuurstofgehalte over een kwartier nog een keer. Je vindt de meting Zuurstofgehalte voor de training bij Zelfzorg onder het kopje Metingen. Zorg ervoor dat je handen warm zijn en haal eventuele nagellak of gelnagels weg. Blijft je zuurstofgehalte lager dan 95%? Overleg dan met je fysiotherapeut of je mag gaan trainen.
Eerste meting (voor de training)	Zuurstofsaturatie 95,1 of hoger	Je zuurstofgehalte is goed, je kan starten met je training. Vergeet niet om na de training je metingen in te vullen!
Tweede meting (na de training)	Zuurstofsaturatie 90 of lager	Je zuurstofgehalte is aan de lage kant. Train morgen iets minder hard en bespreek dit advies met je fysiotherapeut.
Tweede meting (na de training)	Zuurstofsaturatie 90 of hoger	Goed gewerkt, volgende keer weer een stukje beter. Gefeliciteerd!
Pols		
Eerste meting (voor de training)	Hartslag 70 of lager	Je hartslag is wat laag. Doe een lichte warming-up en bespreek dit advies met je fysiotherapeut. Meet na de warming-up nog een keer je hartslag. Je vindt de meting Hartslag voor de training bij Zelfzorg onder het kopje Metingen. Blijft je hartslag lager dan 70? Overleg dan met je fysiotherapeut of je door mag gaan met trainen.
Eerste meting (voor de training)	Hartslag 120 of hoger	Je hartslag is wat snel. Ga even rustig zitten en meet je hartslag over een kwartier nog een keer. Bespreek deze meting met de fysiotherapeut.
Tweede meting (na de training)	Hartslag 100 of hoger	Je hartslag is op dit moment wat hoog. Train morgen iets minder hard en bespreek dit advies met je fysiotherapeut.
Derde meting (30 seconden na de training)	Hartslag 120 of hoger	Kan een foute meting zijn. Als het morgen weer zo is, even met de fysiotherapeut bespreken, alstublieft.
Bloeddruk		
Eerste meting (voor de training)	Bovendruk 200mmHg of hoger	Ga niet trainen, meld deze meting volgende keer bij de fysiotherapeut
Eerste meting (voor de training)	Bovendruk onder de 200mmHg	U kan starten met trainen.
Tweede meting (na de training)	Bovendruk 200mmHg of hoger	Stop met trainen, meld deze meting volgende keer bij de fysiotherapeut
Tweede meting (na de training)	Bovendruk onder de 200mmHg	Goed gewerkt, volgende keer weer een stukje beter. Gefeliciteerd!
Stappenteller	 	1

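### Appendix 3, cited for the limits at which the call center contacts the hospital, does not mark which readings trigger that call, and its reply at systolic 200 mmHg or more defers the report to the next therapist contact

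*Protocol*

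**What the plan says.** **Escalation.** Section 1 (Recruitment) has patients send their vital signs through the app to a call center and continues: "In case of previously set limitations, this call center will contact the hospital (Appendix 3"). The same section (Home-monitored training) cites the appendix for a second purpose: "automatic advises will be given through the app (Appendix 3"). Section 6.3 states: "In case of anomalous measurements, the hospital will be contacted". Section 11.1, item j, adds: "In case of deterioration, treating physician will be contacted". The Summary rests its risk assessment partly on the statement that patients "will be monitored for safety throughout the program".

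**Appendix 3.** Its title describes it as automated answers from the app. For systolic pressure of 200 mmHg or more before training the reply is "Ga niet trainen, meld deze meting volgende keer bij de fysiotherapeut" (do not train; report this reading to the physical therapist next time). After training it is "Stop met trainen, meld deze meting volgende keer bij de fysiotherapeut" (stop training; same report). Below 200 before training it is "U kan starten met trainen" (you can start training).

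**Contact pattern.** Section 6.3 has home training take place in office hours after a communication with the communication center, and has the center give feedback after each session. The therapist is seen once a week, on Wednesday in the example week of Appendix 2.

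**Death rule.** Section 6.7 ends the study when deaths during preparation exceed 10% of included subjects. It does not say whether these are the subjects included so far or the planned 100.

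**The concern.** Home monitoring is the protocol's stated safeguard for people who exercise while waiting for aneurysm repair, and there is no data safety monitoring board. Sections 1, 6.3 and 11.1 promise that a worrying reading reaches the hospital or the treating physician. A reader who follows the citation to Appendix 3 finds cut-offs for messages to the patient, but not the subset that obliges the call center to phone. Section 6.3 leaves an anomalous measurement undefined.

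The one written instruction for very high blood pressure routes the report to the therapist and sets no day for it. In these patients such a reading is one for which a clinician would want to hear promptly. Section 11.1 itself names raised blood pressure as a possible side effect of exercise.

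Section 6.7 raises a smaller question of the same kind: a mandatory rule whose trigger depends on how one phrase is read.

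**Working it through.** **1. Vital-sign rows of Appendix 3**

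| Block | Rows | Abnormal rows | Abnormal rows that refer to the therapist | Rows naming hospital, physician or call center |
|---|---|---|---|---|
| Saturation | 4 | 2 | 2 | 0 |
| Pulse | 4 | 4 | 4 | 0 |
| Blood pressure | 4 | 2 | 2 | 0 |
| Total | 12 | 8 | 8 | 0 |

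Cut-offs are present: saturation 95 before and 90 after training; pulse 70 and 120 before, 100 after, and 120 in the third measurement; systolic 200 before and after. None is marked as a value for calling the hospital.

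**2. Time to the next therapist visit, from the patient message alone.** In the example week of Appendix 2, home sessions are on Monday, Tuesday, Thursday and Friday, and the visit is on Wednesday.

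- Monday: 2 days
- Tuesday: 1 day
- Thursday: 6 days
- Friday: 5 days

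After a Thursday reading of 200 mmHg or more, three home sessions (Friday, Monday, Tuesday) come before the visit. The automated reply allows each to start if that day's reading is below 200.

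**3. Overlap at 90.** One post-training saturation row covers 90 or lower and advises lighter training; the other covers 90 or higher and congratulates. A reading of exactly 90 meets both.

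**4. Section 6.7, minor point.** The rule acts when deaths / base > 0.10.

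- Planned base of 100: 10/100 = 10% does not exceed the limit and 11/100 does, so eleven deaths are needed.
- Base of subjects included so far: 1/9 = 11.1% exceeds the limit and 1/10 = 10% does not, so one death suffices if at most nine subjects have been included when it occurs.

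The protocol gives no preoperative death risk, so 1% and 2% are assumed, with independent deaths.

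| Reading of the base | Stops at 1% | Stops at 2% |
|---|---|---|
| Planned 100, P(X ≥ 11) | below 0.001% | 0.0006% |
| Running count, each outcome known before the next inclusion (exact recursion, n = 1 to 100) | 9.1% | 18.4% |
| Running count, staggered inclusion (simulation) | about 6–7% | about 13–14% |

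The simulation assumes regular inclusion of about 1.0 to 1.2 subjects per week (100 within two years is about one per week) and death at a uniform time within a preparation of 3 to 9 weeks. The lower figures arise because more subjects have usually been included by the time an early subject dies. For example, one death when 12 are included is 1/12 = 8.3%, which does not trigger the rule.

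**The case against.** The strongest reply is that Appendix 3 consists of texts shown to the patient, and such texts need not name a call that staff make. The appendix does contain numeric cut-offs, so these could be the limits that section 1 means, with section 6.3 supplying the action. That reading is not excluded, and it defeats the stronger inference that the appendix contains no limits at all. What stands is that nothing says which cut-offs lead to a call. Some plainly should not: a resting pulse of 70 or lower is on the list.

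A reader might also infer that a reading of 200 mmHg goes without action. It does not: both messages halt exercise at once, and only the report is deferred.

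Nor is the wait of one to six days the delay that the protocol as a whole prescribes. Section 6.3 places the communication center before and after each session, training is confined to office hours, and Table 2 budgets for app alerts. The wait describes the patient message alone. It would become real if the center had no limit to act on, and the protocol supplies none.

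On section 6.7, it is fair to say that an early stop errs towards caution, that section 7.1 already obliges suspension on safety grounds, and that section 7.2.2 sends each death to the ethics committee within 7 days. It does not follow that any death among the first nine subjects ends the study; that depends on how many have been included by then. Imposing a minimum number is a choice, not the correction of an error. Only the undefined base remains.

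**Conclusion.** The point holds as an incomplete safety instruction and should be fixed. The protocol promises hospital contact at set limits, cites Appendix 3 for them, and there marks no value as a trigger: 0 of 12 vital-sign rows name the hospital, the physician or the call center, and 8 of 8 abnormal rows point to the therapist. The reply at systolic 200 mmHg or more stops training correctly but sits badly with the promised hospital contact, because the report may wait up to six days in the example week if the communication center does not step in. The overlap at 90 is a certain but small error. The documents do not show that the call center works without limits: a separate instruction may exist, and then the citation in section 1 points to the wrong place.

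The death-rule point is minor. The trigger lies anywhere between one early death and eleven deaths, depending on how the base is read. Running-count stop rates of about 6–9% at an assumed 1% risk and 13–18% at 2% depend on the pace of inclusion and should be read as illustrations. No endpoint or analysis is affected by either point.

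**What to change.** **Appendix 3 and section 1**
- Mark in Appendix 3 the values at which the call center contacts the hospital: at least systolic 200 mmHg or more and low saturation, with the limits set by clinicians. If these limits are in a separate call-center instruction, cite that document in section 1 instead.
- In both 200 mmHg replies keep the instruction not to train or to stop, and replace the report next time with contact on the same day.
- Make the post-training saturation rows exclusive, for example below 90, and 90 or higher.

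**Section 6.7 (minor)**
- State whether included subjects means those included so far or the planned 100.
- A minimum number before the rule applies is optional. With a running count applied from 20 subjects (then at least 3 deaths), the stop rate under the exact recursion falls from 9.1% to 0.3% at an assumed 1% risk and from 18.4% to 2.2% at 2%. It also falls from 87% to 78% at 10%, where stopping is wanted, and the first 19 subjects would rest on case review under section 7.1.

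**Cost.** A small amendment: a few edited rows, one citation and one sentence. The downside is a few more calls to the hospital. Sample size, endpoints and analysis are unchanged.

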UAVG Dutch Act on Implementation of the General Data Protection Regulation;

in Dutch: Uitvoeringswet AVG

VAT Ventilatory Anaerobic Threshold

WMO Medical Research Involving Human Subjects Act; in Dutch: Wet Medisch-

wetenschappelijk Onderzoek met Mensen

SUMMARY

Rationale: An aneurysm of the abdominal aorta (AAA) is a potentially life-threatening condition. Growth control and preventive surgery are important. It is proven safe to train patients with an AAA aiming to enhance aerobic fitness and improve surgical outcomes. Hypothesis: Training of patients awaiting their surgery for an AAA improves preoperative aerobic fitness. However, not all patients will improve their aerobic fitness following these training sessions.

Objective: The main objective is to separate patients who benefit from training from patients who do not benefit from training in terms of the change in CoF. The secondary objective is to study if training leads to change of aerobic fitness (CoF) in AAA patients after supervised training with a patient-specific training program. Feasibility of the study will be evaluated as well.

Study design: This is a single-arm intervention study. Patients, elected for AAA surgery, are invited to participate in this study. After inclusion, patients' socio-economic and personal characteristics are collected in a questionnaire, as well as their comorbidities (frailty-score, daily activities, ASA-score, dietary habits). All included patients will train at home under the responsibility of the principal investigator and the remote supervision of a specialist in sports medicine and a physical therapist, using home monitoring by means of the Luscii app. **Study population:** Patients with an indication for elective AAA surgery (endovascular and open surgery). Excluded are patients with AAA and an urgent (within less than 3 weeks) repair of the aneurysm and ruptured or symptomatic patients. Patients with genetic connective tissue disorders (e.g., Marfan) and patients unable to train will be excluded as well

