Intervention: Patients who signed informed consent (IC) for this study must fill out a questionnaire, with the assistance of a research nurse and perform a cardiopulmonary exercise test (CPET). Patients rejected from training will be excluded. This is evaluated by the cardiologist and the specialist in sports medicine. Subjects fit for training start with home monitoring (pulse oximeter and sphygmomanometer) under the remote supervision of a physical therapist. All patients will be supported with dietary substitution to avoid a catabolic condition preceding the operation. Before and after three-to-nine-week (on average six weeks) training program, subjects are evaluated by a specialist in sports medicine, to evaluate CoF with a CPET. All patients will be followed until three months postoperative.

Main study parameters/endpoints: The main endpoint is the analysis of patients who improve from training compared to patients who do not improve from training. Secondary endpoints are:

- change in oxygen uptake (VO2) at the ventilatory anaerobic threshold (VAT) after the training program.
- program feasibility (recruitment rate, adherence, completion rate, drop-out rate, attrition rate, and adverse events).
- the (preliminary) effect of the program on other cardiopulmonary exercise testing (CPET) values, e.g., VO2 at peak exercise, oxygen uptake efficiency slope, and response profiles, as well as strength improvement.
- Postoperative events will be compared in relation to the subgroup analysis of patients benefiting from training or not.

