5. NON-INVESTIGATIONAL PRODUCT

Not applicable, neither a medicinal, a food product, nor a chemical compound will be investigated.

Version number: 4 20 of 41

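### Everyone receives supplements alongside training, yet the secondary objective credits the pre-post change to training, and the nutritional component is not described in one consistent place

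*Protocol*

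**What the plan says.** **What participants receive.** The design statement in Protocol section 1 makes added nutrition part of the single-arm pre/post study. Its paragraph on nutritional supplementation sets out three components:

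- protein "immediately following exercise and (approximately 30 minutes) before sleep, providing a standard dosage of 30 g of a high-quality (whey and casein) protein";
- vitamin D: "It will be supplemented daily according to guidelines of the Health Council of the Netherlands";
- for the rest, "all other vitamins and minerals are supplied in a multivitamin/mineral supplement containing 50% of the recommended daily allowance".

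The Summary (Intervention) says that "All patients will be supported with dietary substitution to avoid a catabolic condition preceding the operation". The Summary's text on burden and risks says that "The extra energy and proteins necessary for the training will be substituted with extra FortiFit". The Recruitment text in section 1 says that fit subjects receive "an explanation how to use the home monitoring app Luscii and FortiFit".

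**What the treatment sections say.** Section 3.1 describes the treatment as a questionnaire and exercise. Section 3.2, on co-interventions, mentions only adjustment of cardiac medication. Section 5 is marked not applicable because "neither a medicinal, a food product, nor a chemical compound will be investigated". Section 6.3 counts three explanations to the patient (monitoring, questionnaires, training); nutrition is not one of them.

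**What the result is credited to.** The Summary objective reads: "The secondary objective is to study if training leads to change of aerobic fitness (CoF"), after supervised training. The secondary objective in the Objectives section is the preliminary effectiveness of a home-monitored training programme. Section 8.2 tests the before/after difference in VO2 at VAT with a paired t-test or Wilcoxon signed rank test. Section 6.2 confirms that there is no randomisation.

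**The concern.** The protocol gives the supplements a physiological purpose: section 1 says that the protein is there to support muscle protein synthesis. They are therefore meant to act on the patient's condition during the same weeks as the training. If VO2 at VAT rises, the objective as worded invites the conclusion that training raised it. The data cannot show that, because no participant trains without supplements or takes supplements without training.

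The second part is descriptive. A reader of the final report, or a centre wishing to repeat the programme, needs to know what was given. Section 1 holds the only regimen with amounts and timing, and its key amount can be read in two ways. The sections where a reader would look for the treatment do not mention it.

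**Working it through.** **1. Attribution.** The inputs are the single arm (sections 1 and 6.2), supplements for all patients (Summary; section 1) and the paired comparison (section 8.2).

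Write the mean paired change as

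mean change = T + N + O,

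where T is the contribution of training, N that of nutrition (any joint effect can be put in either term), and O everything else that differs between the two tests, such as repeat testing, adjusted cardiac medication or the passage of time. Training and nutrition are both present for every patient by design, so the paired test estimates only the sum. For illustration, take the 1.5 ml/kg/min that section 2.4 assumes as the mean improvement, and set O to zero. Any N between 0 and 1.5 with T = 1.5 − N gives the same data, the same test statistic and the same p value. A larger sample does not change this. The protocol gives no figure from which N could be bounded.

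**2. Where nutrition appears.**

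| Place in the protocol | Nutrition |
|---|---|
| Summary, Objective | not mentioned; change credited to training |
| Summary, Intervention | dietary support for all, no product |
| Summary, burden and risks | FortiFit for energy and protein, no amount or timing |
| Objectives, secondary objective | not mentioned; training programme |
| Section 1, design statement | part of the design |
| Section 1, Recruitment | FortiFit explained to patients |
| Section 1, Nutritional supplementation | protein, vitamin D, multivitamin; FortiFit not named |
| Section 3.1 | absent from the treatment |
| Section 3.2 | absent from the co-interventions |
| Section 5 | not applicable; no food product under investigation |
| Section 6.3 | absent from the three explanations |
| Section 8.2 | absent from what the programme is said to use |

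The product name and the regimen are never tied together, and the treatment, co-intervention and procedure sections omit both.

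**3. The protein amount.** The inputs are 30 g and two moments (section 1, Nutritional supplementation), and five sessions a week (section 1, Home-monitored training: four at home and one with the physical therapist). I assume that the sessions fall on separate days and that the bedtime intake applies on all seven evenings.

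- 30 g at each intake: 30 × (5 + 7) = 360 g/week.
- 30 g per day in total: 30 × 7 = 210 g/week.
- Ratio: 360 / 210 = 1.71. Difference: 360 − 210 = 150 g/week.

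The protocol states no weekly total against which to check either reading.

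**The case against.** The strongest reply is that this is largely editorial. The design statement names nutrition, the Summary lists dietary support under Intervention, section 4 says that prehabilitation is tested, and sections 6.1.2 and 8.2 use that wider word. The primary objective compares improved with non-improved patients, so attribution bears mainly on a secondary aim that the protocol itself calls preliminary. A dosage with a stated amino acid content, attached to two named moments, may well mean each intake.

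Much of this stands. The effect is not credited to training everywhere, and the point is confined mainly to the secondary pre-post result. However, the wider word does not settle the matter: section 8.2 lists sports-medicine advice, physical-therapist consultations and eHealth monitoring as what the programme uses, and leaves nutrition out. Per intake may be the natural reading of 30 g, but the text does not say so.

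A reader might infer more than the protocol supports:

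- *That FortiFit is the only supplement in some sections.* Neither mention excludes other products, and FortiFit may be the protein product in section 1. Its composition is not given. These are unlinked descriptions, not rival regimens.
- *That section 5 denies giving a food product.* It says only that none is under investigation, which is compatible with giving one as support.
- *That some centres would withhold vitamin D and the multivitamin.* Silence in a summary is not an instruction to withhold, and only section 1 sets out a regimen.
- *That weekly protein could be 420 g (30 × 2 × 7).* This needs a post-exercise intake every day, which does not fit five sessions a week.
- *That intake goes unrecorded because the Appendix 1 log has no field for it.* The case report forms (section 10.1) are not shown, so this does not follow.

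**Conclusion.** The concern holds in a limited form. Every participant receives supplements during the training period, the Summary and the secondary objective credit the change in VO2 at VAT to training, and a single-arm paired comparison cannot separate the two. This rests on the stated design alone and needs no numerical assumption. The share of any change that might be due to nutrition cannot be estimated from the protocol.

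The description of the nutritional component is also incomplete across sections. The one numerical consequence is the weekly protein amount, 360 or 210 g, under the assumption of five training days and seven evenings. The protocol does not settle which is meant, and this review takes no position.

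Sample size and the choice of test are unaffected. The change should be made because it alters what the secondary result can be said to show.

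**What to change.** 1. In the Summary objective, the secondary objective and section 8.2, describe the quantity as the change in VO2 at VAT observed during the combined training-plus-nutrition programme, and word the conclusion in the same way. Claiming an effect of the combination would still go too far, because an uncontrolled before/after change cannot be causally attributed to the combination either.
2. Reconcile the Summary (Intervention; burden and risks), section 1 (design statement, Recruitment, Nutritional supplementation) and sections 3.1, 3.2, 5 and 6.3 into one description of the nutritional component, and refer to it from the other places. It should state whether 30 g is per intake or per day, and how FortiFit relates to the listed supplements. The responsible clinicians decide the content.

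The cost is protocol wording only. The downside is a narrower conclusion, about the programme as delivered and not about training.
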